***Pharmacokinetic analysis***

All concentration measurements after single and multiple dosing are tabulated by time point and treatment group and listed. Reasons are explained for any missing measurements and measurements not included in the pharmacokinetic analysis.

Descriptive statistics for concentration measurements and PK parameters include the mean, standard deviation, the median, the minimum, the maximum, coefficient of variation (%), and the number of valid cases (N). Geometric means and geometric coefficient of variation are also presented for concentrations and PK parameters such as C and AUC.

The actual values of sampling time are used to calculate individual values of PK parameters using the noncompartmental approach. The dependence of drug concentration on time is presented graphically for each individual patient based on actual sampling time. The descriptive statistics and average PK curves are presented based on the estimated sampling time points. Average and individual PK curves are presented on the arithmetic and logarithmic scale.

**Name of active substance:**PBTZ169 Hydrochloride

---

***Pharmacokinetic and pharmacodynamic analysis***

An additional analysis is carried out to compare pharmacokinetic and pharmacodynamic parameters.  $C_{\max,ss}$  and  $AUC_{0-24,ss}$  measured after multiple dosing after 14 days of therapy are used for early bacterial activity  $EBA_{0-14}$  and  $EBA_{2-14}$  as parameters for PK comparison.  $C_{\max}$ ,  $C_{\min}$ , and  $AUC_{0-24}$ , measured after the first dose administration are used for early bacterial activity  $EBA_{0-2}$ .

PK/PD indicators are compared using graphical representation (plotting pairs of individual values against on X and Y for each comparison of parameters X and Y) and by calculating coefficients of correlation within treatment group as well as in general.

An interim analysis is to be carried out when at least 15 patients across all groups have completed the study. The interim analysis is not carried out since the study is terminated early.

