**Name of active substance:**

PBTZ169 Hydrochloride

---

State Budgetary Health-Care Institution of the Arkhangelsk Region Arkhangelsk Clinical Tuberculous Dispensary Address: [name] Principal investigator: [name]

Study Center 9:

Regional State Budgetary Health-Care Institution Tomsk Phthisiatric and Pulmonologic Medical Center Address: [name] Principal investigator: [name]

Study Center 10:

State Health-Care Institution of the Samara Region Tolyatti Municipal Tuberculous Dispensary Address: [name] Principal investigator: [name]

Study Center 11:

Federal State Budgetary Institution Novosibirsk Tuberculosis Research Institute of the Ministry of Health Care of the Russian Federation Address: [name] Principal investigator: [name]

Study Center 12:

State Autonomous Health-Care Institution Republican Clinical Tuberculosis Dispensary Address: [name] Principal investigator: [name]

Study Center 13:

Federal State Budgetary Institution Saint Petersburg Research Institute of Phthisiopulmonology of the Ministry of Health Care of the Russian Federation Address: [name] Principal investigator: [name]

**Publications (references):** none**Phase of drug development:** IIa

**Goals:** to study the efficacy of PBTZ169 in the daily doses of 160, 320, and 640 mg based on its early bactericidal activity, safety, and pharmacokinetics of PBTZ169 p.o. as monotherapy for 14 days in patients with newly diagnosed microbiologically proven respiratory tuberculosis with preserved susceptibility to Isoniazid and Rifampicin.

**Design:** this study is a randomized open-label study of efficacy (in terms of early bactericidal activity), safety, and pharmacokinetics of PBTZ169 in parallel groups with active control in patients with newly diagnosed respiratory tuberculosis. The study comprises the following stages:

**Name of active substance:**PBTZ169 Hydrochloride

---

---

- Screening, up to 10 days
- Monotherapy, 14 days
- Follow-up, 7 days

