**Name of active substance:**

PBTZ169 Hydrochloride

---

Nocturnal sputum is collected from all subjects in the morning at V1. After that, every patient received the study drug (PBTZ169 or isoniazid) as a monotherapy for 14 consecutive days. After 14 days of monotherapy (Day 15 of the study, V8), PBTZ169 is discontinued in Groups 1 to 3 (Day 14 being the day of the last PBTZ169 dose). Standard therapy is initiated 3 days after the monotherapy end date (Day 18 of the study, V10). Standard therapy drugs are resumed in Group 4 (standard dose of isoniazid) without a break—that is, the day following the monotherapy end date (Day 15 of the study). Patient monitoring during clinical study is continued on a hospital basis and ended 7 days following the monotherapy end date.

Venous blood samples are taken from all subjects in Groups 1, 2, and 3 (PBTZ169 monotherapy) to measure PBTZ169 levels. Blood samples are drawn before the first dose of PBTZ169 (0 min time point) and later at the following time points after the first dose: in 0:20, 0:40, 1:00, 1:30, 2:00, 2:30, 3:00, 4:00, 6:00, 8:00, 10:00, 12:00, and 24:00 (hr:min). Blood samples are also taken before the last dose of PBTZ169 (0 min time point) and later at the following time points after the last dose: after 0:20, 0:40, 1:00, 1:30, 2:00, 2:30, 3:00, 4:00, 6:00, 8:00, 10:00, 12:00, 24:00, 48:00, and 72:00 (hr:min).

All venous blood samples are kept in case any additional parameters have to be measured.

Subjects are hospitalized throughout the monotherapy and follow-up periods.

**Number of subjects:** It's planned to randomize 52 eligible subjects for the study, namely 15 subjects in each PBTZ169 group and 7 subjects in the isoniazid group.

The data of subjects who will receive at least one dose of the study drug and whose study drug concentrations are known will be processed in the final statistical analysis of efficacy and pharmacokinetics.

The data of subjects of ITT population will be processed in the final statistical analysis of safety.

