**Pharmacodynamics:**

- $C_{\max,ss}$  and  $AUC_{0-24,ss}$  measured after multiple dosing after 14 days of therapy are used for early bacterial activity  $EBA_{0-14}$  and  $EBA_{2-14}$  as parameters for PK comparison.

$C_{\max}$ ,  $C_{\min}$ , and  $AUC_{0-24}$  measured after the first dose administration are used for early bacterial activity  $EBA_{0-2}$  as parameters for PK comparison.

**Name of active substance:**PBTZ169 Hydrochloride

---

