***Efficacy analysis***

According to the EMA Guidance, early bactericidal activity (EBA) assessment should be based on determining the count of live mycobacteria in the patient's sputum during monotherapy with the drug. The primary method of determining mycobacterial count used is inoculating agar with sputum to count CFU/mL. The method is chosen as it is used as the primary method in nearly all studies assessing early bactericidal activity, which means it can be considered conventional [16–19].

The method of quantitative PCR for counting mycobacterial cells in sputum is used as a secondary method for secondary analysis [23].

All assessments of  $\log_{10}$  CFU/mL sputum, mycobacterial cell count estimates obtained with PCR, and their changes from baseline are tabulated by measurement points and treatment groups.

In the primary analysis of treatment efficacy, changes from baseline in  $\log_{10}$  CFU/mL sputum (for agar inoculation) 14 days after the therapy start date are estimated. Changes in  $\log_{10}$  CFU/mL sputum 2 and 7 days after the therapy start date are also estimated in the secondary analysis of treatment efficacy. Early bactericidal activity (EBA) is assessed as a change in  $\log_{10}$  of CFU/mL of sputum specified for the treatment day [24] with a two-sided 95% confidence interval.

Though sample size is estimated empirically disregarding formal comparisons between the two dose levels, the Kruskal–Wallis test is used to compare the values for different dose levels of the study drug at a two-sided 5% significance level.

The history of mean changes in  $\log_{10}$  CFU/mL from baseline by assessment points is presented graphically by treatment groups.

The Jonckheere–Terpstra test is used to identify the trend for the primary efficacy endpoint depending on the increase in dose level (increasing  $EBA_{0-14}$  for increasing doses).

A similar efficacy analysis (based on changes in  $\log_{10}$  cells/mL) is carried out by determining mycobacterial cell count with quantitative PCR.

Graphical methods and calculation of correlation coefficients between individual measurements obtained using the two quantification methods are used to analyze the

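### Beyond scatter plots, the additional PK/PD analysis summarises exposure and EBA only by correlation coefficients; no slope or model with a confidence interval is planned.

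*Combined protocol and SAP*

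**What the plan says.** The synopsis section Pharmacokinetic and pharmacodynamic analysis opens by giving the work supporting status: "An additional analysis is carried out to compare pharmacokinetic and pharmacodynamic parameters". It then names two methods. The first is graphical: "PK/PD indicators are compared using graphical representation (plotting pairs of individual values against on X and Y for each comparison of parameters X and Y". The second is numerical: "by calculating coefficients of correlation within treatment group as well as in general". It does not state the type of correlation (Pearson or rank) or the scale (raw or log). It plans no regression, slope, interval or exposure-response model.

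The parameter pairs are set out there and under Pharmacodynamics. Steady-state Cmax and AUC0-24 "measured after multiple dosing after 14 days of therapy are used for early bacterial activity" over days 0-14 and 2-14; first-dose Cmax, Cmin and AUC0-24 go with EBA0-2.

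Three other places bear on the point.

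- **Goals:** the trial is "to study the efficacy of PBTZ169 in the daily doses of 160, 320, and 640 mg based on its early bactericidal activity", together with safety and pharmacokinetics.
- **Number of subjects:** enrolment is set out in one sentence: "It's planned to randomize 52 eligible subjects for the study, namely 15 subjects in each PBTZ169 group and 7 subjects in the isoniazid group".
- **Efficacy analysis:** EBA is the change in log10 CFU/mL with a two-sided 95% confidence interval. In addition, "the Kruskal–Wallis test is used to compare the values for different dose levels of the study drug at a two-sided 5% significance level", and a Jonckheere–Terpstra "test is used to identify the trend for the primary efficacy endpoint depending on the increase in dose level". Both tests work on dose group, not on measured exposure.

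**The concern.** The trial gives three doses over a 4-fold range and takes a full concentration profile after the first and last dose in every PBTZ169 patient: 14 samples around the first dose and 16 around the last. Such data can estimate how much EBA changes per unit of exposure. A correlation coefficient cannot, for three reasons.

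1. It has no units, so it does not say how many log10 CFU/mL are gained per doubling of AUC.
2. It depends on the spread of exposure. Within one dose group the spread is narrow and r is small; across doses it is wide and r is larger. The two planned coefficients can differ although one relation produced both.
3. It does not separate a steady rise from a relation that levels off.

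What is at stake is the usefulness of the PK/PD result for choosing doses to carry forward, and the chance that a weak within-group r is taken to mean no effect of exposure at a given dose.

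**Working it through.** **Plan's own figure.** 3 × 15 + 7 = 52, which agrees with the stated total. PBTZ169 concentrations are measured only in Groups 1 to 3, so at most 45 exposure–EBA pairs are available, 15 per dose. The documents give no figure for the PK/PD analysis itself and no SD, CV or effect size. All values below marked as assumed are therefore not from the plan.

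**Step 1: one relation, two coefficients.** Assumed: EBA (taken as the fall in log10 CFU/mL) rises by b = 0.5 per doubling of AUC; exposure is proportional to dose and log-normal. On the log2 scale the doses lie at −1, 0 and 1, with variance 2/3. The within-dose variance is s² = ln(1 + CV²)/(ln 2)².

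- r within a group = b·s / √(b²s² + SD²)
- r overall = b·√(s² + 2/3) / √(b²(s² + 2/3) + SD²)

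For CV 40%, s² = 0.309. With SD 0.8, r within = 0.278/√(0.077 + 0.64) = 0.328, and r overall = 0.494/√(0.244 + 0.64) = 0.525.

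| Assumed CV | Assumed SD | r within | r overall | Slope |
|---|---|---|---|---|
| 40% | 0.8 | 0.328 | 0.525 | 0.5 |
| 40% | 1.0 | 0.268 | 0.443 | 0.5 |
| 60% | 0.8 | 0.447 | 0.581 | 0.5 |

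A simulation over a wider range (CV 20–60%, SD 0.5–1.1; 1,500 trials per setting) gave mean within-group r from 0.12 to 0.61 and overall r from 0.36 to 0.75. The fitted slope stayed at 0.49–0.50.

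**Step 2: shape.** The same simulation was run with EBA rising by 1 log10 between the typical 160 mg and 320 mg exposures and flat above. Overall r was 0.31–0.58, against 0.36–0.75 for the steady rise. The ranges overlap, so r alone does not tell the two apart.

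**Step 3: precision of r.** Fisher 95% limits are tanh(atanh r ± 1.96/√(n − 3)). For r = 0.3 they are −0.25 to 0.70 at n = 15 and 0.01 to 0.55 at n = 45.

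**Step 4: precision of a pooled slope.** The 95% half-width is approximately t × SD / √(n(s² + 2/3)), before baseline adjustment.

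- n = 45, CV 40%, SD 0.8: 2.017 × 0.8/√(45 × 0.976) = 0.24
- n = 45, CV 40%, SD 1.0: 0.30
- n = 45, CV 60%, SD 0.8: 0.21
- n = 15 in total (illustrative, for early termination), CV 40%, SD 0.8: 2.160 × 0.8/√(15 × 0.976) = 0.45

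**Step 5: can a curvature term show levelling off?** Assumed: 1 log10 per doubling up to the typical 320 mg exposure, then flat; CV 40–60%, SD 0.8–1.0. A quadratic term reached p < 0.05 in about 39–69% of simulated trials with 45 patients, and in about 14–24% with 5 per dose.

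**The case against.** A reader might infer that exposure is related to EBA by correlation alone, and that the plan has no means of showing levelling off between 160 and 640 mg. The documents do not support that. The sentence that plans the coefficients first plans plots of individual value pairs, and such plots can show direction and a possible plateau by eye. The Efficacy analysis also gives EBA by dose in the right units with 95% intervals, plus two tests across doses. That is the randomised comparison, and it shows coarsely whether the higher doses add anything. Within a dose, exposure is not randomised and may be confounded, for example by body weight or disease severity. All of this stands and limits the point to the numerical summary of the exposure relation.

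Nor does the plan test the correlations for significance, so a comparison of the chance of p < 0.05 within group and overall would criticise a test that is not there. Reporting both coefficients also lets an alert reader see the effect of range.

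It is fair, too, that this is an additional analysis with an empirically chosen sample size, in a study that the synopsis says was terminated early. Plots and correlations are a defensible exploratory choice, and a fitted model would be imprecise. This lowers the importance but does not remove the point: with few patients a within-group r is very poorly determined, whereas a pooled slope uses every PBTZ169 patient and shows its uncertainty in its interval.

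What remains is that neither the plots nor the by-dose results give an estimate, with an interval, of how EBA changes with measured exposure.

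**Conclusion.** The point holds as an improvement to a supporting analysis. The planned coefficients carry no effect size and depend on the spread of exposure: in the central assumed case one relation gives 0.33 within a group and 0.53 overall, while the slope is 0.5 per doubling, with a 95% half-width of about 0.21 to 0.30 at 45 patients and about 0.45 at 15 (SD 0.8, CV 40%). These sizes rest wholly on assumed slope, SD, CV and dose proportionality; the qualitative conclusion does not.

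It would be too much to conclude that the trial cannot address dose-response or that its efficacy conclusions are affected. The primary endpoint is analysed separately, by dose group. It would also be too much to expect the added regression to settle whether the higher doses lie on a plateau, since a curvature term has limited power even at full enrolment.

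**What to change.** Add, as the main numerical PK/PD result, one pooled linear regression across all PBTZ169 patients of EBA0-14 on log2 AUC0-24,ss, adjusted for baseline log10 CFU, with log2 Cmax,ss in a second model. Report the slope per doubling with its 95% confidence interval, and the predicted EBA0-14 with interval at each dose group's geometric mean exposure (geometric means are already planned in the Pharmacokinetic analysis). Do the same for EBA0-2 with first-dose AUC0-24.

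Keep the plots and both sets of correlations as descriptive output, and state the type and scale of the correlation. Use the plots to check the log-linear form. Treat any quadratic term as exploratory with low power, and do not rely on an Emax fit.

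State that exposure within a dose is not randomised and that precision depends on the number actually enrolled. Label the analysis post hoc if results are already known.

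The cost is a few lines of analysis text on data already being collected. The downside is that a log-linear form is assumed.
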